### 6 months ( $\pm 15$ days)

A member of the research team will call or email the family and ask questions about any problems the child has had, dependent on the treatment option, with their appendix or surgery since their 30-day follow-up. Any recurrence or other complications will be discussed. Also, additional missed days from school and work will be assessed as well as any additional out-of-pocket expenditures (e.g. insurance copayments, and outpatient medications), if any. A \$30 VISA® ClinCard will be provided after successful completion of the 6 month follow-up. The gift card will be mailed to the legal guardian's address.

Data will also be collected from additional chart review and claims data. This will include: appendicitis recurrence with determination of simple vs. complicated appendicitis from operative and pathology reports; subsequent ED visits or physician visits; subsequent readmissions and reoperations; additional imaging, pharmaceutical, and laboratory procedures related to their chosen appendicitis treatment, if any.

### 1 year ( $\pm 30$ days)

A member of the research team will call or email the family and ask questions about any problems the child has had, dependent on the treatment option, with their appendix or surgery since their 6-month follow-up. Any recurrence or other complications will be discussed. Also, additional missed days from school and work will be assessed as well as any additional out-of-pocket expenditures (e.g. insurance copayments, and outpatient medications), if any. A \$35 VISA® ClinCard will be provided after successful completion of the 1 year follow-up. The gift card will be mailed to the legal guardian's address.

The child and legal guardian will also complete the PEDSQL Quality of Life Inventory: Child and Parent Report, and the legal guardian will complete the Satisfaction with Decision Scale.

Data will also be collected from additional chart review and claims data. This will include: appendicitis recurrence with determination of simple vs. complicated appendicitis from operative and pathology reports; subsequent ED visits or physician visits; subsequent readmissions and reoperations; additional imaging, pharmaceutical, and laboratory procedures related to their chosen appendicitis treatment, if any.

Subjects who turn 18 during the study, will be verbally consented.

#### Annually ( $\pm 30$ days)

A member of the research team will call or email the patient and/or family on an annual basis. This will help us determine the rates of recurrence and long term surgical complications beyond the 1 year follow up that has been performed in prior studies regarding non-operative management and appendectomy for appendicitis.

A \$50 VISA® ClinCard gift card will be provided after completion of their 2 year and 3 year follow-up evaluations

#### Participants who choose non-operative management

For the participants who have chosen non-operative management, we will continue to contact them annually in order to access the inherent risks of choosing non-operative management.

## **5. Statistical Considerations**

### 5.1. Primary and Secondary Endpoints

#### Patient Centered

Primary patient centered endpoints are decision self-efficacy immediately after the patient and caregiver have made their decision regarding operative or non-operative treatment (within one hour of the decision) and healthcare satisfaction at discharge.

Secondary patient centered endpoints are preparedness for decision making and caregiver activation level immediately after the patient and caregiver have made their decision, recall (knowledge) immediately after the patient and caregiver have made their decision and at 30 days follow-up, decision regret at discharge and 30 days follow-up, decisional conflict immediately after the patient and caregiver have made their decision, reasons for initial choice at discharge, satisfaction with decision and health care associated costs at 30 days and 1 year, and health related quality of life (HRQOL) prior to discharge and 30 days after discharge.

#### Medical

The primary medical endpoint is disability days at 1 year. Disability days is a composite of inpatient hospital days, emergency department visits, primary care physician visits and all days with limited activities referable to their appendicitis.

Secondary endpoints are disability days at 30 days and 6 months, readmission rate and length of stay. We also hope to determine the rate of recurrence of acute appendicitis for those patients who opt to receive antibiotic therapy and the rate of surgical complications for patients undergoing appendectomy. This outcome will be measured at the aforementioned time points, and will also be measured on an annual basis.

## 5.2. Statistical Methods

Patient-centered endpoints to be analyzed using mixed models across all time points at which the measure was determined are total decision self-efficacy scores, total PedsQL™ healthcare satisfaction generic module scores, and total PedsQL™ HRQOL general core scale scores in patients and caregivers. Time will be included as a categorical variable in each of these models, and its interaction with the PAT intervention will also be included. The interaction terms will provide estimates of the differences in these patient-centered outcomes between PAT and standard surgical consultation arms at each time point in the study. An unstructured error covariance approach will be used to account for the within-subject correlation in outcomes measured over time.

For disability days in a year, we will test for non-inferiority with a margin of less than two days. It is possible that the PAT will reduce disability days. The non-inferiority test can be followed by a superiority test for disability days, with no effect on Type I error. The PAT and standard surgical consultation groups will also be compared on their average readmission rates. We will assume a negative binomial distribution using GENMOD procedure in SAS 9.3 to model the count of days.

### Subgroup Analyses

We will perform exploratory subgroup analyses to examine outcomes that are relevant only to either the operative or non-operative treatment groups. This will be especially useful if we find a difference in disability days between the randomized groups, because the difference may be related to differences in the percentage of patients within the PAT group compared to the standard surgical consultation group that choose operative vs. non-operative management.

Within the subgroup of patients that choose operative therapy, we will compare post-operative infections, re-operation rate at one year, and readmission rate at one year to identify if receiving the PAT altered these medical outcomes.

Within the subgroup of patients who chose non-operative therapy, we will examine the need for appendectomy during initial admission, recurrence of appendicitis at one year, and antibiotic side effects at 30 days to identify if receiving the PAT altered these outcomes. Proportions will be compared for antibiotic complications, recurrence, post-operative infection, and complications. Average readmission rates will be compared using a Pearson chi-square test.

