## 2.2 Secondary Objective

The secondary objective is to characterize the effects of a PAT on medical outcomes from appendicitis in patients receiving the PAT compared to those receiving standard surgical consultation alone. We will determine differences in disability days, length of stay, readmission rates, and medical complications related to treatment choice (e.g. infection, recurrence).

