#### *Phase 2:*

After the development of a PAT, we will conduct a prospective, single-blind, single-site, randomized trial to determine if providing patient-caregiver dyads with a PAT improves decision making and patient centered outcomes without compromising medical outcomes compared to standard surgical consultation alone in pediatric patients (7-17 years old) with early appendicitis and their caregivers. The patient-caregiver dyads and the physician research members administering the PAT will not be blinded. All clinicians subsequently interacting with these patients will be blinded as to whether the patient received the PAT or not.

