##### Study Procedures:

### Consultation

All randomized patients will be approached by a trained physician research member who will conduct the consultation prior to meeting the surgeon.

Patient-caregiver dyads randomized to the standard consultation will receive only verbal information regarding the two treatment options (operative or non-operative management) with patients having the opportunity to ask questions. This type of consultation is akin to a typical surgical consultation in which surgeons verbally inform patients of their options and elicit questions.

A trained physician research member will administer the PAT among patient-caregiver dyads randomized to the PAT and then answer questions about the risks and benefits of each treatment option. If the child is in 5th grade or higher, they will have the option of having their own tablet to watch the PAT.

After the physician research member has answered all patient and caregiver questions, the patient-caregiver dyad will choose either appendectomy or non-operative management. Discrepancies between the caregiver's choice and the patient's choice will be recorded, but the caregiver, by law, will make the decision. Both arms will complete computer-based questionnaires that measure patient and caregiver recall, caregiver activation, preparedness for decision making, decision self-efficacy, and decisional conflict after the treatment choice has been made. Any patient or caregiver who wishes to speak with a member of the surgical team prior to making a decision will be able to do so.

The physician research member will then inform the clinical team of the treatment choice and the surgeon will be called to speak with the family for a full discussion of the care plan and to obtain surgical consent if operative management was chosen.

The patient will be admitted to the hospital and receive care according to standard protocols for either appendectomy or non-operative management of appendicitis. Based on the results of our pilot study, we have demonstrated that non-operative management is a reasonable alternative to appendectomy for cases of early, acute appendicitis. As such, we are presenting both options as initial treatment options for early acute appendicitis to patients and their caregivers.

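### Section 5.2 compares the arms within the treatment chosen after the PAT and reads the result as whether the PAT altered complications; those contrasts are not randomised and can only be descriptive

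*Protocol*

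**What the plan says.** Under section 4, Consultation, the PAT or the verbal consultation comes first: "After the physician research member has answered all patient and caregiver questions, the patient-caregiver dyad will choose either appendectomy or non-operative management". Randomisation has already taken place (section 4, Screening and Enrollment).

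Section 5.2, Subgroup Analyses, then plans "exploratory subgroup analyses to examine outcomes that are relevant only to either the operative or non-operative treatment groups". Among operative choosers it compares "post-operative infections, re-operation rate at one year, and readmission rate at one year to identify if receiving the PAT altered these medical outcomes". Among non-operative choosers it examines appendectomy during the initial admission, "recurrence of appendicitis at one year, and antibiotic side effects at 30 days to identify if receiving the PAT altered these outcomes".

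The same section says that a disability-day difference between arms may reflect "differences in the percentage of patients within the PAT group compared to the standard surgical consultation group that choose operative vs. non-operative management". Section 6.2.1, Consultation with PAT, lists as a risk that the tool could lead families to a different decision.

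Section 2.2 sets the objective "to characterize the effects of a PAT on medical outcomes from appendicitis in patients receiving the PAT compared to those receiving standard surgical consultation alone" and gives infection and recurrence as examples of the complications to be compared. Outside the subgroups, section 5.2 names arm-level medical comparisons only for disability days and readmission.

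**The concern.** The subgroup variable is measured after the intervention and may be affected by it. Families who choose antibiotics after seeing the PAT need not resemble those who choose antibiotics after a verbal consultation. A difference in recurrence between these two sets may come from who chose, not from anything the PAT did to the course of disease. No difference would not be evidence of no effect either, because a within-choice contrast cannot register an effect that acts through the choice itself, a route the protocol names.

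Reporting these rates within treatment is reasonable, since most of the events belong to one treatment and section 5.1 asks for such rates. The fault is the stated inference, which appears twice. What is at stake is the section 2.2 objective and, for these itemised events, the Phase 2 aim of improving decisions "without compromising medical outcomes compared to standard surgical consultation alone".

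**Working it through.** **Plan figures.** Subgroup Analyses states no figure to reproduce. The nearest stated figure, 80% non-inferiority power (section 5.3), reproduces: 2 / (5 × √(2/100)) = 2.828; 2.828 − 1.960 = 0.868; Φ(0.868) = 80.7%. It does not enter what follows.

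**Inputs from the protocol.** 100 dyads per arm (section 3.2.2). In the pilot, 80% of children first treated non-operatively did not need appendectomy (section 1.2), so failure is 1 − 0.80 = 20%.

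**Assumptions (not in the protocol).** Control share choosing non-operative care 30%, 50% or 70%. Half the children are at 30% failure risk and half at 10%, averaging 20%. The PAT has no effect on any child's failure risk. It moves 20% or 50% of the operative choosers in one risk half to non-operative care.

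**Step 1: selection bias within non-operative choosers.** PAT-arm rate = (control failures + movers × their risk) / (control choosers + movers). At a 50% share there are 50 operative choosers, 25 per risk half, so 5 or 12.5 move.

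- Higher-risk movers: (10 + 1.5)/55 = 20.9%; (10 + 3.75)/62.5 = 22.0%. Bias +0.9 or +2.0 points.
- Lower-risk movers: (10 + 0.5)/55 = 19.1%; (10 + 1.25)/62.5 = 18.0%. Bias −0.9 or −2.0 points.
- If movers come equally from both halves, their risk is 20% and the bias is 0.

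| Control share | Movers | Bias, either direction (points) | Within-choice 95% half-width (points) |
|---|---|---|---|
| 30% | 7 / 17.5 | 1.9 / 3.7 | 17.8–19.6 |
| 50% | 5 / 12.5 | 0.9 / 2.0 | 14.6–15.4 |
| 70% | 3 / 7.5 | 0.4 / 1.0 | 12.8–13.2 |

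Half-width = 1.96 × √(p₁(1−p₁)/n₁ + p₂(1−p₂)/n₂).

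**Step 2: a more extreme pattern.** Let the risk halves shift differently. Control: 50% of each half chooses non-operative care. PAT: 20% of the higher-risk half and 60% of the lower-risk half do. The PAT-arm rate is (0.5×0.2×0.30 + 0.5×0.6×0.10)/(0.5×0.2 + 0.5×0.6) = 0.06/0.40 = 15%, against 20%. The bias is 5 points, and a nominal 5% test rejects in about 9% of trials.

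**Step 3: what a whole-arm contrast measures.** With 20% failure in both arms and the share rising from 50% to 60%, 70% or 80%, appendectomy after a non-operative choice goes from 10 per 100 to 12, 14 or 16. The within-choice difference stays at 0. The 2 to 6 points equal share times failure rate. That is a different estimand, not a bias in the planned contrast.

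**Step 4: total appendectomies.** In the lower-risk case at a 50% share, failures rise from 10 to 10.5 or 11.25 per 100. Total appendectomies fall from 50 + 10 = 60 to 45 + 10.5 = 55.5, or to 37.5 + 11.25 = 48.75. In Step 3 at an 80% share they fall from 60 to 20 + 16 = 36.

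**Step 5: precision of whole-arm estimates.** With 100 per arm, half-widths are 7.1 (6% v 8%), 8.7 (10% v 12%), 9.0 (10% v 14%) and 9.3 points (10% v 16%). Two-sided 5% power for the last three is about 7%, 14% and 24%.

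**The case against.** Four arguments count against the point.

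- **The analyses are called exploratory, carry no alpha and touch no primary endpoint.** This stands as a limit on severity. It does not make a post-intervention subgroup contrast show what the intervention altered.
- **Section 2.2 already commits to an arm comparison of complications, and its method may sit in a SAP.** This stands. A reader might infer that the protocol leaves out the randomised comparison of infection and recurrence. It does not: the comparison is a stated objective, and the absence of a method from section 5.2 is not in itself an error. What a SAP cannot excuse is the inference that the protocol does state.
- **Effects acting through choice are sought elsewhere, in whole-arm disability days and readmission.** Largely true, and those cover part of the burden. They do not cover the itemised events, and length of stay, though listed as an endpoint, has no arm-level method in section 5.2 either.
- **The bias is assumed and small.** True. Choice share, risk split and movement are all assumptions, and sampling noise is several times larger.

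A stronger reading is also tempting: that the planned analysis would show benefit while harm increased, because within-choice failures fall as whole-arm failures rise (Steps 1 and 4). The documents do not support it. Appendectomy after trying antibiotics is not a net harm when every operative chooser has an appendectomy anyway, and total appendectomies fall in those examples.

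**Conclusion.** The point holds as a fault of inference. Section 5.2 gives a causal purpose to contrasts within a choice that follows the PAT and that the protocol says the PAT may change. They can describe outcomes by arm and treatment but cannot show that the PAT altered them.

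The documents do not determine the size of the bias. It is zero if choice shifts equally across risk, 0.4 to 3.7 points in either direction under the Step 1 assumptions, and 5 points in the more extreme pattern. All are small beside half-widths of about 13 to 20 points. A reader might infer that the trial's main conclusions are at risk. They are not, because section 5.3 rests them on decision self-efficacy, satisfaction and whole-arm disability days. No stated alpha, power or sample size changes. The point is minor to moderate.

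**What to change.** In section 5.2:

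1. Delete the purpose clause that ends each of the two within-choice sentences. Present all within-choice results, antibiotic side effects included, as descriptive rates per arm.
2. To serve section 2.2, also report infection, re-operation and recurrence to one year by randomised arm in all dyads, each singly with a confidence interval, beside the share choosing each treatment by arm.
3. If appendectomy after an initial non-operative choice is reported by whole arm, show total appendectomies with it, and do not read a rise as harm by itself, because it equals choice share times failure rate.
4. Make no whole-arm comparison of antibiotic side effects. The contacts at 2–5 and 10–14 days that ask about oral antibiotics go only to non-operative families (section 4, Follow-Up), so ascertainment would differ with choice.

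Cost: two deleted clauses and three or four added estimates. Chart and claims review already covers all participants at 30 days, 6 months and 1 year and lists recurrence and reoperations. Post-operative infection is already a planned outcome, but the chart-review list should name infection explicitly. The added estimates are imprecise (half-widths of about 7 to 9 points and power of about 7% to 24% in the cases shown). The gain is an estimate protected by randomisation, not a powered test.

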## 5.3. Sample Size and Power

Our sample size is 200 total patient-caregiver dyads.

The primary patient centered outcomes are decision self-efficacy immediately after the patient and caregiver have made their choice regarding operative or non-operative treatment (within one hour of the intervention) and healthcare satisfaction at discharge. We expect the PAT will increase the total Decision Self- Efficacy Scale score by 0.4 standard deviations, and increase total PedsQL™ healthcare satisfaction generic module scores at discharge by 0.5 standard deviations. Assuming that we will show superiority for one or both of these patient centered outcomes, we also consider it critical to claim that the PAT does not increase the number of disability days over a year as compared to standard surgical consultation. Based on our previous research and published data, we expect the number of disability days in the standard surgical consultation group to be 14 days with a standard deviation of 5 days. Based on this, we set our noninferiority margin to 14%, or two days more. For the primary patient centered outcomes we will use Holm's procedure to test the two primary outcomes. Non-inferiority of disability days will only be meaningful if we achieve significance on these

primary outcomes. Given this, we plan to use a gatekeeping fallback procedure, whereby we can test for non-inferiority at the one-sided 0.025 level when we achieve significance for one or both of the patient centered primary outcomes. If we fail to reach significance on these primary outcomes, then we will have to use a much more stringent alpha of 0.005 (fallback). In order to use this procedure, our significance level for the patient centered primary outcomes will be set at 0.02 (rather than 0.025).

Based on this strategy, 100 patients in each group will provide power of 92% to reach significance on either primary patient centered outcome, and 74% power to reach significance on both, assuming the effect sizes listed above. This sample number provides 80% power to claim significant non-inferiority of less than two days. Over 200 patients who meet eligibility criteria for the proposed study are admitted to Nationwide Children's Hospital (NCH) annually. Therefore, a 50% annual recruitment rate should ensure adequate enrollment.

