##### 3.2.2. Total Number of Subjects Projected and Site

A total of 200 patient-caregiver dyads (100 in each arm) are projected to be enrolled. The study will be conducted at Nationwide Children's Hospital (NCH). Eligible patients will be recruited and consented during their initial surgical evaluation in the emergency department.

Follow-up research visits will be conducted either by phone, email, at the outpatient surgical center of Nationwide Children's Hospital (NCH), or at the Center for Surgical Outcomes Research (CSOR) within the

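### Section 5.3 pairs Holm with release of the full alpha to non-inferiority after a single success, so family-wise error can reach about 4.5% against an intended 2.5%

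*Protocol*

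**What the plan says.** Protocol section 5.3 sets four rules for three hypotheses: decision self-efficacy, healthcare satisfaction, and non-inferiority on disability days over one year.

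- Procedure for the first two: "For the primary patient centered outcomes we will use Holm's procedure to test the two primary outcomes".
- Their level: "our significance level for the patient centered primary outcomes will be set at 0.02 (rather than 0.025" in the protocol's words.
- Non-inferiority after at least one success: "we can test for non-inferiority at the one-sided 0.025 level when we achieve significance for one or both of the patient centered primary outcomes".
- Non-inferiority after no success: "we will have to use a much more stringent alpha of 0.005 (fallback" is the wording used.

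The design inputs are effects "by 0.4 standard deviations, and increase total PedsQL™ healthcare satisfaction generic module scores at discharge by 0.5 standard deviations", control-arm disability days expected "to be 14 days with a standard deviation of 5 days", and a margin given as "we set our noninferiority margin to 14%, or two days more". Section 3.2.2 gives the size: "A total of 200 patient-caregiver dyads (100 in each arm) are projected to be enrolled". The power stated in section 5.3 is 92% for at least one patient-centered outcome, 74% for both, and 80% for non-inferiority. Section 5.2 adds a superiority test on disability days after non-inferiority and says that this leaves Type I error unaffected.

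**The concern.** Because 0.02 + 0.005 = 0.025, and the 0.02 is set in place of 0.025, the three hypotheses appear to share a single one-sided budget of 0.025. Holm uses all of its 0.02 inside its own family: once one outcome is significant at 0.01, that 0.01 moves to the other outcome, which is then tested at 0.02. Nothing is free to leave the family until both hypotheses are rejected. The plan nevertheless passes 0.02 to non-inferiority after the first rejection. The two remaining tests then run at 0.02 and 0.025 together, although only 0.025 is available for both.

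On the protocol's own figures this branch is a likely one: exactly one outcome succeeds in about 92% − 74% = 18% of trials. If the PAT really helps one outcome only, the trial may falsely claim the second benefit, or falsely claim that the PAT does not add disability days. Section 5.3 calls that no-increase claim critical.

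**Working it through.** **Inputs.** From sections 5.3 and 3.2.2: n = 100 per arm; effects 0.4 and 0.5 SD; SD 5 days; margin 2 days; Holm at 0.02 (steps 0.01, then 0.02); non-inferiority at 0.025 or 0.005. The correlation between the two patient-centered outcomes is not given, so it is assumed and varied.

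**Step 1: the plan's own power.** The expected z-values are 0.4 × √50 = 2.83, 0.5 × √50 = 3.54 and, for non-inferiority, 2 / (5 × √0.02) = 2.83.

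- Non-inferiority at one-sided 0.025: Φ(2.83 − 1.96) = 80.7%. The stated 80% is reproduced. At 0.005 the power is 60.0%.
- One-sided Holm at 0.02, at least one / both: 96.5% / 72.3% at correlation 0, and 92.6% / 74.6% at 0.5. The stated 92% / 74% is reproduced at about 0.5.
- Two-sided Holm at 0.02 gives at most 67% for both, at correlations up to 0.8, so it does not reproduce the 74%.

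The stated powers therefore fit one-sided tests with full Holm recycling inside the 0.02.

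**Step 2: error when no hypothesis should be rejected.** Both outcomes null and the excess at the margin, under independence: 1 − 0.99 × 0.99 × 0.995 = 2.48%. The rule is sound here.

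**Step 3: error when exactly one patient-centered outcome truly improves, excess at the margin.**

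- Limit, with the true effect almost surely significant: 1 − 0.98 × 0.975 = 4.45%. The Bonferroni bound is 0.02 + 0.025 = 4.5%.
- Satisfaction only, 0.5 SD: the probability of significance at 0.01 is Φ(3.54 − 2.33) = 0.887. If it is significant, the error is 0.0445. If not, it is 1 − 0.99 × 0.995 = 0.01495. Total: 0.887 × 0.0445 + 0.113 × 0.01495 = 4.1%.
- Self-efficacy only, 0.4 SD: the probability is Φ(2.83 − 2.33) = 0.692. Total: 0.692 × 0.0445 + 0.308 × 0.01495 = 3.5%.

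Simulation with 2 to 4 million draws agrees and adds correlation:

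| True state (excess at the margin) | Rule as written | 0.025 only after both |
|---|---|---|
| Neither outcome improves | 2.2–2.5% | 2.2–2.5% |
| Satisfaction only, 0.5 SD | 3.9–4.2% | 2.4–2.5% |
| Self-efficacy only, 0.4 SD | 3.4–4.0% | 2.2–2.5% |
| One outcome surely significant | 4.1–4.5% | 2.4–2.5% |

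The ranges cover outcome correlation 0 and 0.5, and correlation of disability days with the outcomes from −0.3 to 0.5. With disability days independent, the two middle rows of the first column narrow to 4.1–4.2% and 3.5–3.8%.

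**Step 4: the superiority test.** If it is run at the level passed to non-inferiority (an assumption, since section 5.2 gives no level), the same sum applies when disability days are truly unchanged. The other outcome at 0.02 and superiority at 0.025 again give 4.45% in the limit.

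**The case against.** Four points can be made for the plan.

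- **The 4.5% is a maximum.** It needs one effect large enough to be almost surely detected, the other exactly null, and an excess exactly at the margin. This stands: at the planned effects the figure is 3.5–4.2%, about 1.4 to 1.7 times the intended level. When both outcomes truly improve, the false non-inferiority rate is about 2.4%.
- **No single claim exceeds its own nominal level.** In the 0.5 SD case, the false non-inferiority claim occurs in about 2.3% of trials and the false second benefit in about 1.9–2.0%. This also stands: the excess is in the chance of making at least one of them. That joint chance is what Holm and gatekeeping exist to limit.
- **The protocol never states a 2.5% family-wise level.** Non-inferiority could be read as a condition attached to a benefit claim, and a false joint claim of benefit and no excess days does stay within 2.5%. But a stand-alone fallback at 0.005, and a reduction from 0.025 to 0.02 made to pay for it, make sense only if one budget covers all three tests.
- **An analysis plan or the cited fallback method might give a different algorithm.** Section 5.3 nonetheless fixes both the levels and the trigger, so the rule must be judged as written.

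**Conclusion.** The concern holds. The release rule in section 5.3 is valid after both successes and invalid after one. Family-wise error in the strong sense is up to 4.45–4.5% against an intended 2.5%, and 3.5–4.2% at the planned effect sizes when only one of the two outcomes improves. The mechanism and the bound do not depend on the unstated correlation. The figures at planned effects assume an outcome correlation of 0 to 0.5 and independent disability days; allowing dependence between disability days and the outcomes widens them to about 3.4–4.2%. The stated powers are not wrong in themselves, but the 80% for non-inferiority presupposes testing at 0.025. Overall power under the written rule is 79.2% at correlation 0.5 (0.926 × 0.807 + 0.074 × 0.600) and 80.0% at 0. This must be corrected, because it is the decision rule for the trial's main claims.

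**What to change.** State the one-sided family-wise level of 0.025 explicitly and replace the release rule with one of the following.

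- **(a) Release after both.** Keep Holm at 0.02. Test non-inferiority at 0.025 only if both patient-centered outcomes are significant, and otherwise at 0.005. In the least favourable case the error is 1 − 0.98 × 0.995 = 2.49%. Power for the patient-centered outcomes is unchanged. Non-inferiority power falls from 79.2% to about 75.4% at correlation 0.5 (0.746 × 0.807 + 0.254 × 0.600), and from 80.0% to 75.0% at correlation 0.
- **(b) Graphical procedure.** Start at 0.01 / 0.01 / 0.005, each rejected hypothesis passing its alpha in equal shares to those remaining. After one patient-centered success, the other outcome is tested at 0.015 and non-inferiority at 0.010. In the least favourable case the error is 1 − 0.985 × 0.990 = 2.49%. Non-inferiority power is 76.7% at either correlation. At correlation 0.5, power for at least one and for both outcomes rises slightly, to 93.4% and 75.6% from 92.6% and 74.6%.

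Option (a) is the smaller edit; option (b) loses less non-inferiority power. Dropping Holm's recycling and passing 0.01 per success would also hold 2.5% and keep non-inferiority power at 77.5%, but power for both outcomes falls to about 65%.

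Run the superiority test of section 5.2 at whatever level non-inferiority received, as part of the same procedure, and restate the non-inferiority power with the assumed correlation. No patients are added. The rule should be fixed before outcomes are compared by arm, since choosing between 0.005 and 0.025 afterwards could be driven by the data.
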